10.4 Objectives and endpoints

The objectives and endpoints for Module 1 can be found in Section 3.

10.5 Module 1 Study Design

Module 1 is an open label, multicentre module to evaluate the preliminary efficacy and safety of RXC004 monotherapy in RNF43 LoF mutation positive, advanced (unresectable)/metastatic PDAC, that has progressed following one prior systemic approved standard of care treatment for advanced (unresectable)/metastatic PDAC.

Patients will only be eligible for Module 1 if they have a documented RNF43 LoF mutation from either the centralised pre-screening activities or from a recognised panel in agreement with sponsor (see Appendix F and Section 5.8 for more details). CCI

CCI

CCI

CCI

CCI evaluable patients will be enrolled in this module (see Table 14 for definition of evaluable patients).

The primary objective of the module is to assess the preliminary efficacy of RXC004 in terms of PFS rate (%) at 6 months. Tumour assessment will be performed by Investigators every 6 weeks \pm 1 week (relative to the date of initiation of study treatment) for the first 54 weeks, followed by Q12W until radiological disease progression (as defined by RECIST1.1).

Following radiological progression, patients will be followed-up for safety and survival.

The rationale for the study design and endpoints can be found in Section 4. The general study design is summarised in Figure 1.

10.5.1 Rationale for Primary Endpoint

The current approved standard of care treatment for 2nd-line metastatic PDAC is liposomal irinotecan in combination with leucovorin/5-FU. A Phase 3 trial (NAPOLI-1 trial, Wang-Gillam et al 2016) evaluating this regimen reported a PFS rate at 6-months of CCI% with an ORR of 16%. Progression Free Survival (PFS) rate at 6-months is more appropriate (e.g. compared to Objective Response Rate (ORR)) to assess the anti-tumour effect of RXC004 as preclinical data indicate that RXC004 monotherapy used in a direct tumour targeting approach in patients with RNF43 LoF advanced (unresectable)/metastatic PDAC may deliver clinical benefit by a predominantly cytostatic rather than cytotoxic mechanism.

10.5.2 Rationale for Secondary Endpoints

ORR, DCR, PFS, OS and % change in target lesions are appropriate endpoints in an advanced (unresectable)/metastatic PDAC patient population and have been widely used and reported in clinical trials in this population.

10.6 Module 1 Patient Population

Module 1 will recruit male or female patients aged 18 years or older with histologically documented advanced (unresectable)/metastatic PDAC, with a documented RNF43 LoF mutation, that has progressed after one prior approved standard of care treatment for advanced (unresectable)/metastatic PDAC, a Karnofsky performance status ≥ 70 and a minimum life expectancy of 12 weeks.

Prospective approval of protocol deviations to recruitment and enrolment criteria, also known as protocol waivers or exemptions, is not permitted.

10.6.1 Inclusion Criteria

Core- and Module 1 -specific inclusion criteria can be found in Sections 5.1 and 5.2, respectively. Participants are eligible to be included in the study only if all of the core- and Module 1-specific following criteria are met.

10.6.2 Exclusion Criteria

Core exclusion criteria can be found in Section 5.4. There are no Module 1-specific exclusion criteria. Participants are excluded from the study if any of the core exclusion criteria are met.

10.6.3 Lifestyle Considerations

Lifestyle considerations can be found in Section 5.6.

10.7 Study Treatment

Details of RXC004 monotherapy treatment can be found in Section 6. Discontinuation criteria for RXC004 can be found in Section 7.

10.8 Study Assessments

General details of the study assessment and procedures can be found in Section 8.

10.8.1 Schedule of Assessments

Table 15 Module 1 (PDAC) Schedule of Assessments

	Module 1 (PDAC)– Schedule of assessments						
	Pre-Screening ^t	Screening	Cycle 0 (3-7 days)	Cycle 1 (21-day cycle)	IP Discontinuation	30 day follow-up	Survival follow-up
Window	n/a	-28 to -1	D1	D15 ± 1d	Within 7 days of discontinuation	± 3d	q6w ± 1 week
Pre-Screening informed consent							
CC1 [REDACTED] CC1	X						
Genetic screening for RNF43 mutations	X						
Main study informed consent							
Demography & baseline characteristics		X					
Tumour genetic and PD-L1 staining history (optional)			X				
CC1 [REDACTED] CC1				X			
(optional and only applicable if not previously collected during central pre-screening)							
Substance use (smoking and alcohol)			X				

Module 1 (PDAC)– Schedule of assessments							
	Pre-Screening ^t	Screening	Cycle 0 (3-7 days)	Cycle 1 (21-day cycle)	Cycle X Day 1 (21-day cycle)	IP Discontinuation	30 day follow-up
Window	n/a	-28 to -1	D1	D1 ± 1d	± 3d	Within 7 days of discontinuation	± 3d q6w ± 1 week
Medical/surgical history		X					
Oral and dental assessments ^o		X					
Inclusion/exclusion criteria ^u		X					
CCI		X					
CCI							
CCI							
CCI							
Physical examination		X	X	X	X	X	X
Karnofsky performance status		X	X	X	X	X	X
Pregnancy test (WOOCBP only)		(X)	(X)	(X)	(X)		
Baseline and 'on treatment' tumour biopsies (mandatory) ^a		X			X ^g		X (optional at progression)
Vital signs (including height and weight) ^m		X	X	X	X	X	X
Clinical chemistry / Haematology		X	X	X	X	X	X

Module 1 (PDAC)– Schedule of assessments							
	Pre-Screening ^t	Screening	Cycle 0 (3-7 days)	Cycle 1 (21-day cycle)	Cycle X Day 1 (21-day cycle)	IP Discontinuation	30 day follow-up
Window	n/a	-28 to -1	D1	D1 ± 1d	± 3d	Within 7 days of discontinuation	± 3d
ECG^w		X	X	X	X	X	X
Blood samples for bone turnover biomarkers (β-CTX)		X		X	X ^k		
DEXA scan		X			X ^l		
CC1			X		X		
CC1							
CC1				X	X		
CC1					X		
CC1						Cycle 2 only	
CC1				X	X		
CC1					X	X	X
RXC004 PK ^f			X		X		
RECIST 1.1 assessments (CT or MRI) ^j		X				On study tumour assessments should occur q6w ± 1 week (relative to first dose of IP) for the first 54 weeks, followed by q12w ± 1 week until RECIST 1.1 radiological progression ⁿ	
CC1 (mandatory unless unavailable at site) ^p		X				On study CC1 assessment should occur at week 6 ± 1 week and week 18 ± 1 week relative to first dose of IP.	
Vitamin D3 and Calcium supplements						Patients should commence 800 IU vitamin D3 (Cholecalciferol) QD and 1000-1500 mg calcium daily supplements from ICF signature until RXC004 discontinuation	

Module 1 (PDAC)– Schedule of assessments							
	Pre-Screening ^t	Screening	Cycle 0 (3-7 days)	Cycle 1 (21-day cycle)	Cycle X Day (21-day cycle)	IP	30 day follow-up
Window	n/a	-28 to -1	D1	D1 ± 1d	± 3d	Within 7 days of discontinuation	± 3d
Denosumab dosing ^g				120 mg SC denosumab once every month from C0D1 until RXC004 discontinuation			q6w ± 1 week
RXC004 dosing ^y			X (2mg single dose)	Continuous daily dosing (2mg QD)			
RXC004 diary			X		Review at each visit	X	
Concomitant medication		X	X	X	X	X	X
Adverse events		X	X	X	X	X	X
Taste assessment ^s		X			At each visit - only if patient reports dysgeusia		
Survival status and post-discontinuation anti-cancer therapy ^h						X	X

^a Screening (pre-first dose IP) biopsy is a mandatory requirement except in exceptional circumstances in which biopsy is not technically feasible. All patients without a baseline sample must be approved by the Sponsor before starting study treatment. The baseline **CCI** can be a 'fresh newly acquired' biopsy or an **CCI** (from the same site that 'on treatment' biopsy will be taken) and taken after completion of all prior standard of care treatments. In exceptional circumstances where baseline biopsy cannot be scheduled before C0D1, the procedure may be performed before C1D1 after a minimum of 4 days washout from C0D1. A second 'on treatment' biopsy at C1D15 (+ up to 7 days), is also mandatory providing that investigator judges the second biopsy to be technically and clinically feasible. An optional biopsy at progression is encouraged. The Cycle 1 Day 15 biopsy should be collected post-dose and the time of collection should be accurately recorded. RECIST 1.1 target lesions should not be chosen for biopsies.

^b **CCI**
^c **CCI**
^d **CCI**
^e **CCI**
^f Blood samples for PK analysis should be collected as follows (the actual time for each blood draw must be accurately recorded):

Cycle 0: CCI	CCI
Cycle 1, CCI	CCI
Cycle X, CCI	CCI

^g **CCI**

^h Survival and details of first and subsequent therapies for cancer, after discontinuation of treatment, will be collected

ⁱ CT (preferred) or MRI, each preferably with IV contrast. It is strongly recommended to maintain use of the same imaging modality (CT or MRI), acquisition protocol, facility, scanner and

Guidelines: RECIST1.1 scan should be performed within 6 weeks of the first dose of study treatment – preferably as close to the first dose as possible, but if scans were performed for alternate reasons prior to signing consent, these may be used for screening purposes to avoid unnecessary scans, if the patient consents, the scan(s) have been performed within 6 weeks of the first dose of study treatment and all the imaging requirements in the Imaging Acquisition Guidelines have been met.

Optional collection of results from any previous tumour genetic screening and/or PD-1/PD-L1 staining. Results from genetic screening of the following genes will be collected from medical records and recorded in the study database: RNF43, TP53, BRCA1, BRCA2, and KRAS.

ECGs should be performed on Cycle 2 Day 1 and as clinically indicated from Cycle 3 onwards. DEXA scans should be performed on Cycle 4 Day 1, Cycle 7 Day 1 and then every 7 RXC004 cycles thereafter (+/- 3-day window). T-score and bone mineral density for each of the following 3 sites, all of which must be assessed at screening: R^2/L total hip, R^2/L femoral neck, lumbar spine [L1-4].

Height is required at screening only.

Symptomatically stable patients may continue study treatment after RECIST1.1 progression, until either symptomatic progression or second RECIST1.1 progression (relative to the first RECIST1.1 progression on study treatment), if agreed with the Sponsor. Patients who continue study treatment after RECIST1.1 progression should continue RECIST1.1 assessments as per protocol until discontinuation of study treatment. See Section 7.1 for more details.

A dental examination with preventive dentistry if appropriate and an individual benefit-risk assessment is mandatory prior to treatment with denosumab. An initial dental examination may be performed by a member of the clinical team who can assess the need for referral to a dentist for further assessment including any preventative dentistry. A visual oral examination (including tongue, palate, uvula, tonsils, buccal mucosa, lips, gums and parotid duct) should also be performed at baseline and at each scheduled visit where dysgeusia is reported as an AE.

卷之三

卷之三

133

133

All patients must receive denosumab before first dose of RXC004. 120 mg sc denosumab should be administered approximately once every month from C0D1 until RXC004 discontinuation. Investigators may delay subsequent denosumab doses until the next scheduled visit providing that there is no significant increase in β -CTX compared to baseline, according to Investigator judgement.

CC1

CC1 CC1 A taste assessment (consisting of a specific set of questions) will be performed at screening and at each study visit when patient reports dysgeusia. Please see Section 8.3.12 for more details.

Pre-screening is not mandatory for patients with prior documented evidence of a loss of function RNF43 mutation from a panel approved by the Sponsor. If available, the last 2 imaging scans taken prior to the screening scan for this study and/or their reports may be requested for central sponsor review.

Patients must fast (water to drink only) for at least 2 hours prior to taking a dose to at least 1 hour post-dose for all doses. Triplicate ECGs should be collected as follows:

Cycle 0: CCl_4
Cycle 1: CCl_4

At selected sites, ambulatory Holter monitoring will be used on Cycle 0 Day 1 and Cycle 1 Day 5 for central analysis of digital ECG information.

CT, computerised tomography; CCI, clinical classification index; IP, index of probability; D, Day; EG, electrocardiogram; QCI, quantitative coronary angiography; DECI, decision index.

Evaluation Criteria in Solid Tumours version 1.1; SC, subcutaneous; WOCBP, women of child-bearing potential. PK, pharmacokinetic(s); QD, once daily; RECIST 1.1.

10.9 Statistical Considerations

General statistical considerations can be found in Section 9.

10.9.1 Module 1 Sample Size Determination

The method by Frewer et al (Frewer et al 2016), together with the totality of the data collected, will be used to guide go/no-go decision making:

For the population under investigation, the standard of care of liposomal irinotecan in combination with 5-FU/Leucovorin showed a 6-month PFS rate of **CCI**% (NAPOLI-1 trial, Wang-Gillam et al 2016), which will be the **CCI** in our study. An improvement to **CCI**% in 6-month PFS would be considered clinically significant in this patient population (**CCI**). Statistically, the hypothesis that will be tested is $H_0: p < \text{CCI}$ versus $H_1: p > \text{CCI}$, where p is the proportion of patients who live 6 or more months without disease progression. **CCI**

CCI
CCI
CCI If **CCI**

patients or fewer are progression free at 6 months RXC004 would be determined not worthy of further investigation with this patient population. The type I and II error rates associated with this testing are 0.06 and 0.10, respectively. The PFS at 6 months estimates will be used to guide the decision for onward development. The totality of the data, including the results from the secondary endpoints will be used to in the final decision.

Approximately **CCI** patients are expected to be enrolled in order for **CCI** patients to be evaluable.

Note: “Enrolled” means the subject has completed the main study CRF and has been assigned to a treatment arm.

MODULE 2 (BTC)

11 MODULE 2 (RXC004 MONOTHERAPY IN BILIARY TRACT CANCER)

11.1 Background

Biliary tract cancer represents 3% of gastro-intestinal malignancies and is the commonest hepatobiliary malignancy and includes gallbladder (GBC), ampulla of Vater (AVC), and intra-hepatic and extrahepatic cholangiocarcinoma (CCA).

The incidence of biliary tract cancer varies hugely with some regions depicting high prevalence accounted for by high liver fluke infestations where cholangiocarcinoma is more common. Areas with a high prevalence of cholelithiasis correspond to a high prevalence of GBC. Regions where these risk factors are absent have a low incidence of biliary tract cancer.

Approximately 30-40% of patients with newly diagnosed biliary tract cancer have disease that is amenable to curative intent surgery. Adjuvant capecitabine has demonstrated a survival advantage (Primrose et al 2019) with a median overall survival of 51 months compared to 36 months with observation alone. Despite this, the prognosis for BTC remains extremely poor with a 5-year survival rate of approximately 2%. Standard of care treatment of newly diagnosed metastatic BTC is gemcitabine in combination with cisplatin which demonstrated an overall survival of 11.7 months compared to 8.1 months with gemcitabine monotherapy (Valle et al 2010). Recently modified FOLFOX (mFOLFOX) in addition to active symptom control reported a median survival of 6.2 months compared to 5.3 months with active symptom control alone in the 2nd line setting (Lamarca et al 2019)

Approximately 50% of cholangiocarcinomas have known molecular alterations/mutations. A trial of pemigatinib, a fibroblast growth factor receptor (FGFR)-2 inhibitor was evaluated in 2nd/3rd line metastatic cholangiocarcinoma patients with FGFR-2 fusions and reported a 36% ORR and a medium survival of 21 months (Abou-Alfa et al 2020). FGFR2 mutations are exclusively found in intra-hepatic CCA (ICC) and are present in approx. 13% of ICC patients. Ivosidenib, an isocitrate dehydrogenase (IDH)-1 inhibitor reported a median OS of 10.8 months in 2nd/3rd line metastatic cholangiocarcinoma patients with IDH1 mutations. Similar to FGFR2 mutations, IDH1 mutations are found in 15% of CCA patients (Abou-Alfa et al 2020); these genetic aberrations are usually mutually exclusive.

11.2 Module 2 Rationale

RXC004 is a small molecule PORCN inhibitor which reduces Wnt signalling and therefore may offer an opportunity to deliver clinical benefit in tumours that have aberrantly activated Wnt signalling.

While downstream Wnt pathway mutations are rare in cholangiocarcinoma, patient samples have been shown to overexpress Wnt ligands. IHC of patient samples showed Wnt3a, Wnt5a, and Wnt7b were positive in 92.1, 76.3, and 100 % of 38 CCA tissues (Loilome et al 2014). In a separate study of 37 patients, Wnt7B and Wnt10A mRNA was found to be significantly higher in CCA when compared to healthy tissue (Boulter et al 2015). High expression of Wnt5a was associated with worse prognosis (Loilome et al 2014).

Porcupine inhibitors have been reported to be anti-proliferative in several human cholangiocarcinoma cancer cell lines both *in vitro* and *in vivo* (Boulter et al 2015 and Noll et al 2016). In addition, porcupine inhibitors have demonstrated efficacy in two *in-vivo* preclinical biliary cancer models, a GEM model and a TAA-induced rat model (Boulter et al 2015).

RXC004 may offer an opportunity to deliver clinical benefit in patients with advanced (unresectable)/metastatic biliary tract cancer that has progressed following 1st-line standard of care treatment, where there is currently still a high unmet need.

11.3 Benefit-Risk Assessment

11.3.1 RXC004 Risks

The risk assessment for RXC004 monotherapy treatment can be found in Section 2.3.1.

11.3.2 Benefit Assessment

This Module will evaluate RXC004 monotherapy in advanced (unresectable)/metastatic biliary tract cancer patients who have received one prior approved standard of care systemic treatment. RXC004 monotherapy may offer clinical benefit by both a direct tumour targeting mechanism and by an immune-oncology mechanism.

Treatment outcome for advanced (unresectable)/metastatic biliary tract cancer remains poor. First line metastatic treatment of patients with advanced BTC with standard of care gemcitabine in combination with cisplatin or gemcitabine monotherapy results in an overall survival in the range of 8-13 months (Valle et al 2010 and Valle et al 2020). Furthermore, the recently reported Phase 3 TOPAZ-1 study demonstrated that the addition of the PD-L1 inhibitor durvalumab to cisplatin and gemcitabine chemotherapy significantly improved overall survival compared with placebo plus chemotherapy in patients with advanced BTC, with HR 0.80 (95% CI: 0.66, 0.97); p = 0.021 (Oh et al 2022). Modified FOLFOX (mFOLFOX) in addition to active symptom control showed a median survival of 6.2 months compared to 5.3 months with active symptom control alone in the 2nd-line setting (Lamarca et al 2019). The hazard ratio reported was 0.69 representing a 31% reduction in the risk of death. However, not all patients are considered fit enough to receive mFOLFOX as 2nd-line therapy.

Porcupine inhibitors have been reported to be anti-proliferative in several human biliary

cancer cell lines both *in vitro* and *in vivo* (Noll et al 2016, Boulter et al 2015). In addition, porcupine inhibitors have demonstrated efficacy in two *in-vivo* preclinical biliary cancer models, a GEM model and a TAA-induced rat model (Boulter et al 2015). Patient samples have been shown to overexpress Wnt ligands. Two studies have already looked at limited Wnt ligands in a small set of patients. IHC of patient samples in the first study showed Wnt3a, Wnt5a, and Wnt7b were positive in 92.1%, 76.3%, and 100%, respectively of 38 cholangiocarcinoma tissues (Loilome et al 2014). In a second study of 37 patients, Wnt7B and Wnt10A mRNA was found to be significantly higher in biliary cancer when compared to healthy tissue (Boulter et al 2015). High expression of Wnt5a was associated with worse prognosis (Loilome et al 2014).

The Phase 1 study of RXC004 enrolled unselected patients with advanced cancers with a median of three prior lines of treatment. Out of 18 RECIST-evaluable patients, five had SD, in one case lasting for up to 26 weeks. All five of these patients with SD had Wnt-ligand-dependent tumours (three of which were BTC), supporting the hypothesis that RXC004 will have clinical activity in selected tumours that are dependent on Wnt ligand signalling pathways (Cook et al 2021).

Given this preclinical and clinical evidence of involvement of the Wnt pathway in cholangiocarcinoma there is a clear rationale to assess RXC004 monotherapy in advanced (unresectable)/metastatic biliary tract cancer patients.

11.4 Objectives and endpoints

The objectives and endpoints for Module 2 can be found in Section 3.

11.5 Module 2 Study Design

Module 2 is an open label, multicentre module to evaluate the preliminary efficacy and safety of RXC004 monotherapy in patients with advanced (unresectable)/metastatic BTC, that has progressed following 1st line standard of care treatment.

Two dose levels of RXC004 will be evaluated in this Module. In Cohort 1, patients will receive RXC004 2 mg QD. Cohort 2 will evaluate a lower dose of RXC004 1 mg QD, depending on the emerging data observed with the 2 mg dose in Cohort 1. Should the 2 mg fail to show any anti-tumour activity in Cohort 1 that warrants further investigation, as per Section 11.9.1, then this lower dose cohort will not open unless the SMC consider that tolerability issues on 2 mg have compromised the ability to show efficacy. If Module 3 (pembrolizumab combination) and Cohort 2 are open at the same time, then Module 3 will be prioritised, i.e. patients who are eligible for Module 3 should be assigned to Module 3 and not to Cohort 2 of Module 2.

CC1 evaluable patients will be enrolled within each cohort of this module (see Table 14 for

definition of evaluable patients).

The primary objective of the module is to assess the preliminary efficacy of RXC004 in terms of PFS at 6 months. Tumour assessment will be performed by Investigators every 6 weeks \pm 1 week (relative to the date of initiation of study treatment) for the first 54 weeks, followed by Q12W until radiological disease progression (as defined by RECIST1.1). Following radiological progression, patients will be followed-up for safety and survival.

The rationale for the study design and endpoints can be found in Section 4. The general study design is summarised in Figure 1.

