4.4.1.6 RXC004 1 mg Monotherapy Dose

Patients who participate in Cohort 2 of Module 2 will receive RXC004 1.0 mg orally QD. The purpose of this cohort is to further characterise the dose-response relationships for activity and safety and to support the optimal dosage(s) for future clinical development.

In the Phase 1 study, the dosing cohorts were small (see Section 4.4.1.1) and patients were not selected for having Wnt ligand-dependent tumours. The median RXC004 exposure was short (approximately 7 weeks); thus, the AEs described in Section 4.4.1.1 were generally observed during the first 2 treatment cycles. Of the observed AEs, only dysgeusia, a known on-target toxicity of Wnt pathway inhibitors, was observed to be dose-related and 4 out of 6 patients in the 2 mg cohort reported dysgeusia within the first 2 treatment cycles. Cohort 2 of Module 2 will explore whether the lower dose of 1 mg has the potential to deliver clinical anti-tumour activity in patients with BTC, a Wnt ligand-dependent tumour, and whether this lower dose has the potential to reduce incidence of treatment related toxicities such as dysgeusia. The 1.5 mg dose was not selected for this purpose because the PK profiles of the 1.5 mg dose and 2 mg dose show considerable overlap.

Initiation of this lower dose cohort will depend on emerging data from the RXC004 2 mg dose cohort. Should the 2 mg dose fail to show any anti-tumour activity in Cohort 1 that warrants further investigation (as per Section 11.9.1), then this lower dose cohort (Cohort 2 of Module 2) will not open unless the SMC consider that the tolerability of the 2 mg QD dose has compromised its ability to show efficacy.

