 - Unhealed lesions from dental or oral surgery
 9. Patients who are pregnant or breast-feeding
 10. Judgment by the investigator that the participant should not participate in the study if the participant is unlikely to comply with study procedures, restrictions and requirements.
 11. Known active HIV, hepatitis B (HBV), or hepatitis C (HCV) infections. Patients with a resolved HBV infection (defined as presence of hepatitis B core antibody [HBcAb] and absence of HBV surface antigen [HBsAg] or negative on polymerase chain reaction [PCR] for HBV DNA) are eligible. Patients positive for HCV antibody are eligible only if PCR is negative for HCV RNA.
 12. Use of any live or live-attenuated vaccines against infectious diseases (e.g., influenza nasal spray, varicella) within 4 weeks (28 days) of initiation of study treatment. Note: Patients that require COVID-19 vaccination within 4 weeks of initiation of study treatment should receive a non-live vaccine (e.g. one based on mRNA or fully inactivated/genetically modified viruses incapable of replication).
 13. Mean resting corrected QTcF >470 ms, obtained from triplicate ECGs performed at screening.

There are no exclusion criteria specific to Modules 1 and 2. Module 3-specific exclusion criteria are listed below.

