5.5 Module 3 Specific Exclusion Criteria

Participants are excluded from Module 3 (RXC004 + pembrolizumab) if any of the following criteria apply:

14. Patients with any contraindication to the use of pembrolizumab as per approved label (Summary of Product Characteristics or equivalent).
15. Has received prior therapy with an anti-PD-1, anti-PD-L1, or anti-PD-L2 agent or with an agent directed to another stimulatory or co-inhibitory T-cell receptor (e.g., CTLA-4, OX 40, CD137), and was discontinued from that treatment due to a Grade 3 or higher irAE.

16. Has received prior radiotherapy within 2 weeks of start of study treatment or have had a history of radiation pneumonitis. [Note: Participants must have recovered from all radiation-related toxicities and not require corticosteroids. A 1-week washout is permitted for palliative radiation (\leq 2 weeks of radiotherapy) to non-central nervous system (CNS) disease.]
17. Has a diagnosis of immunodeficiency or is receiving chronic systemic steroid therapy (in dosing exceeding 10 mg daily of prednisone equivalent) or any other form of immunosuppressive therapy within 7 days prior the first dose of pembrolizumab in this study.
18. Has severe hypersensitivity (\geq Grade 3) to pembrolizumab and/or any of its excipients.
19. Has an active autoimmune disease that has required systemic treatment in past 2 years (i.e., with use of disease modifying agents, corticosteroids or immunosuppressive drugs). Replacement therapy (e.g., thyroxine, insulin, or physiologic corticosteroid replacement therapy for adrenal or pituitary insufficiency) is not considered a form of systemic treatment and is allowed.
20. Has a history of (non-infectious) pneumonitis / interstitial lung disease that required steroids or has current pneumonitis / interstitial lung disease.
21. Has an active infection requiring systemic therapy.
22. Patients with a history of allogeneic tissue/solid organ transplant.
23. Patients with active infections, including tuberculosis, HIV, HBV, or HCV. Patients with a resolved HBV infection (defined as presence of hepatitis B core antibody [HBcAb] and absence of HBV surface antigen [HBsAg] or negative on PCR for HBV DNA) are eligible. Patients positive for HCV antibody are eligible only if PCR is negative for HCV RNA.

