### 3 INVESTIGATIONAL PLAN

#### 3.1 Overall Study Design and Plan

[figure not shown]
This is Phase II, modular, open label, multicentre, study to evaluate the preliminary efficacy and safety of RXC004 monotherapy in advanced solid tumours that have progressed following standard of care treatment.

The study initially opened with ring finger protein 43 (RNF43) loss of function (LoF) mutation-positive pancreatic ductal adenocarcinoma (PDAC) (Module 1) and biliary tract cancers (BTC) (Module 2). The purpose of Module 3 is to evaluate RXC004 1.5 mg in combination with pembrolizumab in patients with BTC. [CC1] [REDACTED] evaluable patients will be enrolled in each module.

The primary objective of the study is to assess the preliminary efficacy of RXC004 in each module in terms of progression free survival (PFS) at 6 months. Tumour assessment will be performed by Investigators every 6 weeks  $\pm$  1 week (relative to the date of initiation of study treatment) for the first 54 weeks, followed by q12w  $\pm$  1 week until radiological disease progression (as defined by Response Evaluation Criteria in Solid Tumours, version 1.1 [RECIST 1.1]). Following radiological progression, patients will be followed-up for safety and survival.

The general study design is summarized in [Figure 1](#).

Figure 1 - Overall Design

DCR, disease control rate; CCI [REDACTED] ECOG performance status, LoF, Loss of Function, ORR objective response rate; OS Overall survival; PFS progression free survival; KP Kamofsky performance status; RNF43 Ring finger 43; RXC004 Porcupine inhibitor.

The analyses will be conducted independently for each module. The module data will be locked before their analyses. All the populations and endpoints described hereafter must be considered independently for each module.

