#### 4.11.2.1 Progression Free Survival

PFS is defined in Section 3.2.1.1.

Kaplan-Meier analyses will be conducted for each module. Survival plots will be produced to present Kaplan-Meier estimated curves. In addition, the following parameters estimated from the Kaplan-Meier curves will be provided for each group:

- Median PFS and corresponding 95% CIs
- PFS rate at 3, 6 and 12 months and corresponding 90% CIs and 95% CI (one month = 30.4375 days).

PFS will be listed for all patients in the FAS.

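### If the 1 mg cohort of Module 2 opens, the SAP specifies no results by dose cohort and scores its exposure against 2 mg

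*Protocol*

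**What the plan says.** **Protocol.** Section 4.4.1.6 states why the 1 mg cohort exists: to "further characterise the dose-response relationships for activity and safety and to support the optimal dosage(s) for future clinical development". Opening it is conditional: "Initiation of this lower dose cohort will depend on emerging data from the RXC004 2 mg dose cohort". Sections 11.5 and 11.9.1 give each Module 2 cohort its own patient numbers. Section 11.9.1 sets a go/no-go hurdle on the 6-month PFS rate, with error rates of 0.06 and 0.20. Table 10 (Section 6.1.1) assigns 2 mg daily to Cohort 1 and 1 mg daily to Cohort 2.

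**SAP.** Section 3.1 says: "All the populations and endpoints described hereafter must be considered independently for each module". Section 4.11.2.1 says: "Kaplan-Meier analyses will be conducted for each module"; it then asks for estimates per group without saying what a group is. Section 4.2.6 lays out summaries as Module 1 versus Modules 2 and 3. Section 4.11.1.6 rules out subgroups and 4.11.1.2 rules out any model. Section 4.10 computes RXC004 RDI with 2 mg per day for Modules 1 and 2 and 1.5 mg per day for Module 3.

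**Assignment.** Protocol 11.5, repeated in 12.5, says: "If Module 3 (pembrolizumab combination) and Cohort 2 are open at the same time, then Module 3 will be prioritised"; that is, "patients who are eligible for Module 3 should be assigned to Module 3 and not to Cohort 2 of Module 2". Module 3 adds exclusions 14 to 23 (Section 5.5), for example "Has an active infection requiring systemic therapy", and tighter transaminase and haemoglobin limits (Section 5.1). For the monotherapy modules, Section 5.4 says: "There are no exclusion criteria specific to Modules 1 and 2".

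**The concern.** The protocol treats Module 2 as two single-arm evaluations at different doses. The SAP treats it as one unit. Followed literally, the SAP would give one Kaplan-Meier curve and one 6-month PFS rate that mix 1 mg and 2 mg, and that rate could not be set against a hurdle meant for each cohort. Safety and exposure summaries would have the same problem, and the RDI table would show compliant 1 mg patients as under-dosed.

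A second, smaller worry concerns who enters Cohort 2. The priority rule removes every patient eligible for Module 3 while both are recruiting, and it does not name Cohort 1. A difference between the doses could then partly reflect who was enrolled.

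**Working it through.** **1. The plan's own figures.** The 0.06 and 0.20 in Protocol 11.9.1 can be neither reproduced nor refuted, because the sample size, cut-off and both reference rates are redacted. The point does not depend on them.

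**2. Unit of analysis.**
- Protocol 11.5 and 11.9.1: numbers are given per cohort. Section 11.5 also refers to the 11.9.1 rule when deciding, from Cohort 1 data, whether Cohort 2 opens. The hurdle therefore has to be readable on one cohort alone.
- SAP 3.1, 4.2.7 and 4.11.2.1: populations, endpoints, figures and Kaplan-Meier analyses are by module.
- SAP 4.15: the Module 2 enrolment sentence omits the per-cohort qualifier found in Protocol 11.9.1.
- Timing: Protocol Appendix M shows that Cohort 2 came in with version 5.0. SAP Section 1 cites version 6. The SAP therefore postdates Cohort 2, yet its readable text does not mention it, and the readable part of SAP 4.16 lists no decision to drop or merge cohorts.

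Illustration (assumed rates, equal cohort sizes): with 40% and 20% progression-free at 6 months, the mixed rate is (40 + 20)/2 = 30%, which describes neither dose.

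**3. RDI.** SAP 4.10: RDI = cumulative dose / (duration in days × 2 mg) × 100. For a patient who takes 1 mg on every day counted, over d days, this is (1 × d)/(d × 2) × 100 = 50%. Undosed days in Cycle 0 lower it slightly. Every Cohort 2 patient dosed at or below the assigned level therefore falls in the lowest category (0% to under 60%), alongside a Cohort 1 patient who took half the planned dose. With the Table 10 dose as denominator, the same patient scores (1 × d)/(d × 1) × 100 = 100%.

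**4. Confounding under the priority rule (all inputs assumed).** Let f be the share of Module 2-eligible patients who are barred from Module 3, o the share of Cohort 2 enrolled while both are open, and D the barred patients' deficit in 6-month PFS. Cohort 1 is taken as unfiltered.
- Barred share: f in Cohort 1 and o + (1 − o)f in Cohort 2. The difference is o(1 − f).
- Spurious shift, 1 mg minus 2 mg: −o(1 − f)D.
- With D = 15 points and f = 0.10, 0.20, 0.30:
  - o = 0: no shift.
  - o = 0.5: −6.75, −6.0, −5.25 points.
  - o = 1: −13.5, −12.0, −10.5 points.
- If both open together with equal targets, Cohort 2 gains f/(1 − f) of its target by the time Module 3 fills. Then o = f/(1 − f) and the shift is −fD = −1.5, −3.0, −4.5 points.
- If D is negative (barred patients do better), every sign reverses.

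**5. Precision of the contrast (assumed).** With 15 to 30 patients per cohort and 40% versus 20%, two-sided 5% power is 22% to 39% and the 95% interval half-width is 32 to 23 points. Power of 80% would need 82 per cohort.

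**The case against.** The best defence is that pooling is inferred from silence. The word group in SAP 4.11.2.1 could mean dose cohort, the output shells are not among the documents, and SAP 4.2.6 shows that the layout wording is loose in any case. Cohort 2 is also conditional, and the documents do not say that it opened; if it never did, the module is the cohort and 2 mg is its assigned dose. This stands in part: the documents show that a cohort split is not specified, not that the doses will be pooled. It does not rescue the RDI formula, which is explicit.

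On assignment, a reader might infer that Cohort 2 can only ever contain patients barred from Module 3, so that dose-response cannot be answered. The documents do not support that. The rule applies only while both are open, for a period that is not stated. Dose-response is the cohort's stated purpose but is not a row in the readable Section 3 table, and no between-dose test is planned. The contrast is non-randomised and sequential by design. Per-cohort PFS, safety and exposure can still be described.

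A reader might also want the priority rule removed. Prioritising accrual to one module is a legitimate choice, and randomising between Module 3 and Cohort 2 would not make Cohort 2 concurrent with Cohort 1. Limiting Cohort 1 to patients who would have been barred would leave very few: 10% to 25% of an assumed 20 is 2 to 5.

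**Conclusion.** The point holds, provided Cohort 2 opens. The protocol sizes two dose cohorts and the SAP specifies analysis only by module, with no subgroups and an undefined group. The RDI mismatch needs no assumption beyond the documents' own doses: at most 50% where the assigned dose would give 100%.

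The eligibility confounding is real for any period of overlap, but it is secondary. Its size and direction are unknown because the overlap, the barred share and those patients' prognosis are not given. The illustrative shifts run from zero to about 13.5 points, and the upper end needs full overlap and an assumed 15-point deficit. It adds an avoidable selection difference to a comparison that was already descriptive and, at the assumed cohort sizes, imprecise.

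**What to change.** In SAP 3.1, 4.2.6, 4.10 and 4.11:
- Define group, for Module 2, as dose cohort.
- Produce all efficacy, safety and exposure outputs separately for Cohort 1 and Cohort 2, carrying the same layout into the safety tables of 4.12.
- Read each cohort's 6-month PFS rate against the Protocol 11.9.1 hurdle on its own.
- Reconcile the Module 2 RDI denominator in SAP 4.10 with the assigned doses in Protocol Table 10.

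For the priority rule:
- Label any 1 mg versus 2 mg comparison as descriptive.
- Record for each Cohort 2 patient whether entry fell while Module 3 was open, and the reason for Module 3 ineligibility.
- Where the collected data allow, show both cohorts by Module 3 eligibility status. This will be incomplete for Cohort 1: HIV and hepatitis tests are mandatory only in Module 3 (Protocol Table 13), and Module 3 eligibility bloods have a 10-day window (Section 5.1).

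If Cohort 2 never opened, a sentence in SAP 4.16 saying so would settle the matter. The cost is a little extra programming and data recording, with no change to the design or to accrual.
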